
C.2.7. Implication of Findings.

These results were used to design an experimental neuroimaging strategy relevant to carrying out a systematic, detailed examination of meditation dynamics. The proposal addresses a number of important issues derived from our preliminary study and consideration of the literature. These include the necessity of determining: (1) the optimal epoch length and appropriate comparison condition for TM cycling protocol; (2) the spatial distribution of meditation-induced BOLD effects in the brain; (3) the appropriate experimental protocol and statistical analysis methods to probe substates during TM; and (4) the contribution of physiological covariables on the BOLD signal during meditation. This later issue is further addressed by experiments that examine the degree to which the respiratory-induced and meditation-induced BOLD signal changes are independent and separable during the periods of spontaneous breath quiescence.

C.2.8. Summary of Preliminary Research.

We conclude that neuroimaging of meditation is possible and that significant information can be obtained by directly analyzing brain dynamics of two principal substates that have been described by previous research utilizing only indirect measures [9, 20-22]. These two mediation substates are: (1) the progressive de-excitation phase of TM practice, and (2) subsequent periods of maximum physiological quiescence during TM practice, marked by spontaneous breath-quiescence (SBQ, breath periods > 10 sec). We will investigate the first substate in Year 1 and the second substate in Year 2.

D. RESEARCH DESIGN AND METHODS

D.1. Introduction.

This R21 exploratory grant will be carried out in collaboration with the Brain Research Institute's Neuroimaging Laboratory at Maharishi University of Management, Michigan State University and the Neurology NMR Facility at Henry Ford Hospital in Detroit. The grant will be devoted to imaging two principal substates during TM practice that are well-suited to fMRI recording and analysis.

We will acquire standard anatomic scans during an initial 40 minutes period before experimental scans. The anatomic scans include: (1) a 3 plane localizer using a fast gradient echo sequence (TE/TR 1.7/32.1 ms); (2) a volumetric scan (3D Fast RF-spoiled gradient echo sequence with TE/TR 3.7/9.1 ms); (3) a 2D T1-weighted FLAIR scan of the slices to be acquired in the fMRI study (2D fast spin echo sequence with TE/TR 7/26ms), and; (4) an 8-shot EPI sequence of the slices to be acquired (TI/TE/TR 860/5.9/1977 ms). The EPI sequence and T1-weighted slices are used to align the fMRI data with the volume scan. For fMRI studies, we currently use the product EPI sequence with 64 by 64 data acquisition matrix, TE of 30 ms, TR of 2.2 sec, FOV 24 cm, slice thickness of 5 mm. 19 slices are acquired in an interleaved fashion (odd first, then even) for the entire time the paradigm is being performed. Following these standard MR scans subjects will perform a simple motor task cycling run (alternating 45 sec episodes of rest and hand-squeezing). This run represents a positive control for the cycling acquisition and analysis in every run.

D.2.2. Data analysis.

The HFH fMRI facility possesses real time fMRI acquisition and analysis software. [name] [181-183] has developed software for er-fMRI analysis [see also 168, 172, 173, 178]. A data analysis system, similar to the system at MSU/HFH, will be installed at M.U.M. This system will complement the AFNI system already running. The HFH software acquires fMRI images and other physiological data (pulse oximetry, respiration, electrocardiogram) on the same computer, allowing a synchronized time-stamp on all data sets. Each channel of acquired data contains a corresponding data file and a timing file. The time series from these other physiological variables will be used as real-time covariables in multiple linear regression, thereby statistically controlling for the contributions of breath rate and CO₂ to the overall BOLD effect.

The sequence of analysis includes: (1) discarding the initial three scans of each run due to magnetic instability; (2) correcting for movement artifacts by the co-registration of the time series using AIR (automatic image registration); (3) morphing the distorted fMRI image onto the accurate, high resolution MRI anatomic image, by registering fMRI images to the 8-shot EPI scan using AIR and registering the T1-slice to the 3D-volume using image intensity; (4) generation of statistical parameter maps from the *t*-statistics resulting from the multiple linear regression—a statistical parameter map (SPM) is a map of all pixel areas that exceed a specified statistical threshold and; (5) transforming the *t*-statistic maps into *Z*-statistic maps for statistical analysis. With large numbers—100 or more—the *t*-distribution approximates a *Z*-distribution [184]. These final statistical parameter maps will reflect significant fluctuations in signal intensity during the two conditions of the cycling tasks, after the contribution of other physiological variables have been statistically removed.

D.2.3. Statistical analysis.

One of the valuable characteristics of fMRI is that the relatively high signal to noise ratio allows detection of significant changes in signal intensity *within* a single subject [185]. The steps for statistical analysis of all data will include:

- (1) The SPM [184] for the runs in each condition will be examined. Areas of significant signal fluctuations will be determined using two criteria [92]: (a) the *Z*-statistic > 4.0, ($p < 10^{-7}$), and (b) the cluster must contain a minimum of four pixels that touch on the sides or corners (eight-neighborhood connectivity).
- (2) We will examine the first run for possible adaptation effects. If the first run differs significantly from subsequent runs, we will consider excluding the first run from the overall analysis.
- (3) The *Z*-statistic of significant areas of fluctuations in signal intensity are noted when they meet the criteria above and are in 2 of the 3 statistical parameter maps from multiple runs in the same condition.
- (4) These *Z*-statistics will be used in parametric analyses.

D.2.4. Sample size.

We determined the sample size of 10 subjects based on published studies [111, 186]. The fMRI study of Lazar et.al. [143] reported significant results with five subjects. Two PET studies [142, 144] reported significant signal changes with nine and four subjects, respectively. The study of Qigong [187] examined cerebral blood flow using two subjects, but reported no estimates of significance. Newberg et.al. [73] neural SPECT study of Tibetan meditation reported significant blood flow changes with eight subjects. An examination of 50 reports on PET or fMRI imaging of various interventions, including CAM modalities, such as, hypnosis, acupuncture, complex cognitive tasks, or simple sensory and motor stimulation showed that statistical significance was found with 10 or less subjects [see for example, 108, 111, 162, 188, 189-199].

D.3. Timeline.

Over the two years, we will alternate between image acquisition and data analysis to sequentially address our two aims. At the conclusion of the R21, we will have delineated the basic fMRI methodology appropriate for imaging brain mechanisms during TM practice, and will have collected sufficient data to suggest a neural model of brain mechanisms underlying two distinct substates during TM.

Month	Activity Year 1	MRI Sessions
1	Upgrade Neuroimaging Laboratory at M.U.M. (new software and work station; Hire RA; Recruit subjects)	—
2-3	Pre-screen and screen subjects; First runs to estimate effect size; Train RA to use analysis software at HFH and M.U.M.	2
3-12	Aim 1—Expt 1: Determine optimal epoch length and control condition during the cycling protocol	18
10-12	Write and submit papers	
	Total MRI sessions Year 1	20

Subjects will participate in multiple experiments (sessions).

Month	Activity Year 2	MRI Sessions
1-10	Aim 2—Expt 2: Determine BOLD response at the onset of and during intentional Breath-Holding and spontaneous breath-quiescence using er-fMRI and sr-fMRI analysis	20
10-12	Write and submit papers	—
12	Submit RO1s	—
	Total MRI sessions Year 2	20

The screening of 15 subjects will involve minimal recording time and analysis time. The recording time will be just over 1.5 hr for tests (a 5-min motor task cycling-run, TM cycling-runs, and uninterrupted self-paced TM runs) and 40 min for standard anatomic scans. The analysis will determine whether (1) the subject was able to meditate in the magnet as evidenced by breath changes and subjective reports, and (2) the fMRI images are relatively free of physiological and movement artifacts.

D.4. Population Selection.

The communities of Fairfield, IA and Greater Detroit, MI are uniquely suited for this study, with over 3,000 individuals who have been practicing the TM technique from a few months to over 30 years (average 10-20 years). This group ranges in age from 10 to over 80 years. We will attract 100 candidate subjects by email list and advertisement in Fairfield and Detroit. We will *pre-screen* potential subjects in Fairfield and Detroit, and then *screen* subjects with a trial run in the magnet in the HFH Neurology NMR Facility. Subjects will be reimbursed for participating in any of the five experiments detailed below.

D.4.1. Prescreening of subjects.

We will identify 30 subjects from the 100 candidates through the prescreening process, preferably from the Greater Detroit area (60 min driving distance). During pre-screening, subjects will learn about the nature of fMRI recording, the research design, and the inclusion/exclusion criteria. The criteria will be based on factors that may possibly affect measurement of BOLD activity:

- (1) **Basic demographics:** (a) Age 20 to 55 years; (b) All right-handed (Edinburgh test of handedness); (c) English speaking; (d) No alcohol or cigarette use, and; (e) Similar number of men and women.
- (2) **Physiological:** (a) No serious medical conditions; (b) No prescription medication; (c) No learning disabilities; (d) No history of head trauma; and (e) No metal within or on the body (including extensive dental work).
- (3) **Time:** Subjects should be able to participate in the two experiments.
- (4) **Scanner:** No claustrophobia and ability to meditate comfortably
- (5) **SBQ:** Subjects should display SBQ at a rate of 10 per 20min of noncycling meditation.

D.4.2. Screening of subjects.

We estimate 30 subjects will meet the first three criteria. We will then assess medical history and obtain written consent (see Section E). They will be given an audio tape and instructed to practice the TM technique at home with earplugs, lying down in a darkened room, with the audiotape playing the fMRI machine noise. This home practice will accustom subjects to the fMRI experimental conditions. Then, subjects will come to either the HFH or M.U.M. laboratory for a trial run in a cardboard mockup of the MRI

machine with the same audiotape. In the mockup, subjects will practice TM, train with the signaling protocol, with both control conditions (passive listening and mental-counting), and have respiratory and autonomic data acquired, to satisfy the fourth criteria above. Subjects will pass this last two pre-screening criteria, if they are comfortable with the environment and protocol, and demonstrate clear periods of spontaneous breath-quiescence during the trial run. We estimate 20 subjects will qualify for MR imaging.

Of the 20 candidates, we expect about 5 individuals will not meet the final two criteria necessary for inclusion in the study during the first MRI scan at HFH. These two criteria are:

- (6) **MR protocol criteria:** (a) No claustrophobia; (b) No metal placements within or on the body (including extensive dental work); (c) Minimal recording artifacts (e.g., low levels of head movement and tissue inhomogeneity, due to sinus configuration and dental work).
- (7) **Meditation criterion:** Appropriate meditation experience based on subjective reports and respiratory patterns during TM practice in the MRI environment.

We expect that a minimum of 15 subjects will meet the full set of screening criteria and will be the subject pool for the five experiments in this grant. One of the advantages of running the same subjects multiple times is that within- and between-subject variance can be assessed.

D.4.3. Estimation of Sample Size.

We determined sample size of 10 subjects based on published neuroimaging studies [111, 186]. The fMRI meditation study of Lazar et.al. [143] reported significant results with five subjects. Two PET studies of meditation [142, 144] reported significant signal changes with nine and four subjects, respectively. Litscher's recent study of Qigong [187] examined cerebral blood flow using two subjects, but reported no estimates of significance. Newberg et.al. [73] neural SPECT study of Tibetan meditation reported significant blood flow changes with eight subjects. An examination of 50 reports on PET or fMRI imaging of hypnosis, acupuncture, complex cognitive tasks, or simple sensory and motor stimulation showed that statistical significance was found with 10 or less subjects [see for example, 108, 111, 162, 188, 189-199].

D.5. Examine the Patterns of Neural Activity during the De-Excitation Substate (Aim 1).

Experiment 1: Selection of epoch length and control condition to image the de-excitation process.

D.5.1. Hypotheses. We will be testing two hypotheses in this experiment.**D.5.1.1 Epoch length.** We hypothesize that the shorter epoch length in a ABC-cycling protocol (randomly-ordered meditation and controls) will best 'frame' the initial de-excitation process due to significantly higher signal-to-noise ratio, higher signal intensity and less variance in the statistical test;

D.5.1.2. Control conditions. We hypothesize significant differences in signal intensity across the three different epoch conditions—TM, passive-attending and mental-counting, including in rank order: de-excitation will be maximum for TM, then passive-attending, and lastly, mental-counting.

D.5.2. Issues.

D.5.2.1. Epoch length. Epoch length will be pre-framed during our subject selection protocol. We will examine two epoch lengths centered on this preliminary value. The best frame will include maximum duration of the de-excitation process without the actual onset of a SBQ for most of the meditation epochs.

D.5.2.2 Control conditions. Control conditions are an essential component of fMRI cycling. Since cycling runs yield a comparison of change in signal intensity between conditions, e.g. rest versus hand-squeeze or controls versus TM, it is important to carefully choose the comparison condition. The comparison condition ideally should differ along the dimension that best distinguishes the experimental task. Eyes-closed rest (without task instruction) would seem to be an appropriate comparison condition. However, during "rest" there is no control over the subject's cognitive processes. He/she could be daydreaming, engaged in intellectual or emotional mentation, drifting to sleep, or unintentionally settling into TM practice.

To avoid this confound, we will use an 'ABC' cycling protocol, comprising eyes-closed, randomly ordered epochs of (A) TM, (B) passive-attending to nature sounds, and (C) mental-counting by '2s'. Both controls minimally engage the subject attention, yet should help prevent them from either settling into meditation or drifting asleep, which can occur during simple eyes-closed rest condition. Counting is similar to TM in that both these eyes-closed conditions involve simple repetitive mental activity. Counting differs from meditation along a salient cognitive dimension—counting requires vigilance and attention to the counting process, while during TM practice, the attention automatically follows the thought process during de-excitation [3]. However, the counting-by-2's may activate specific brain areas. Eyes-closed mental arithmetic (reciting single digit multiplication tables and serial subtraction) has been found to activate pre-motor, frontal and parietal cortical areas [200]. We assume counting by 2's will not be as difficult a task as the above multiplication and subtraction. They require extensive activation of frontal areas that play an executive role in utilizing the semantic memory of arithmetical facts. The second control--eyes-closed passive-attending to audiotaped nature sounds--may more closely match the meditation cognitive dynamics of de-excitation. The primary difference being that in meditation the attention is moving in an 'inward' direction (effortlessly attending to internal experience) in comparison to the passive-attending control in which the attention is more 'outwardly' directed (i.e., listening to external stimuli). In conclusion, it will be important to compare the effects of passive-attending and mental-counting on fMRI during TM cycling runs.

D.5.3. Method.

We will record fMRI (in first 10 subjects meeting inclusion criteria) during randomly ordered epochs of controls and TM practice. We will use two cycling ABC-run with eyes-closed. Each ABC-run comprises TM and two control conditions: (1) listening passively to nature (ie, ocean) sounds or (2) mental-counting by '2s'. An ABC-run (for example, using 30 sec epochs) will last about 22min, including 45 total epochs, 15 epochs each condition. This will result in 22 min/run x two epoch lengths = 45 min of testing, plus 40 min of preliminary anatomic scans, for a total time of less than 2 hr per MRI session. Whole-brain scans will be recorded from 19 slices per scan. At the end of each 22-min run, subjects will be asked to report their experiences. Carryover effects will be minimized by: (1) inserting one minutes breaks between runs. During these breaks we will be speaking and de-briefing the subjects; and (2) randomly presented control conditions in the same run. With this design, *within*-sets comparison will provide an estimate of the *minimal* carryover effects and *across*-sets will provide an estimate of *maximal* carryover effects.

D.5.4. Analysis for Hypotheses 1 & 2.

The data will be processed, and clusters of significant fluctuations in signal intensity will be noted (see Sect. D.2.2-D.2.3.). We expect clusters of fluctuations in signal intensity in 4-8 brain areas (see Sect. B.). The Z-statistics for areas of significant fluctuations in signal intensity will be noted from all runs and used as the variate in a repeated measures MANOVA. In this MANOVA, brain areas (4-8 estimate), and epoch condition (3) will be the factors, and the epoch-lengths (2) will be the repeated measure. For all main effects, individual comparisons will be conducted.

1. We expect **main effects for brain areas**, indicating significant differences in signal intensity between one or more brain areas. These changes may include in rank order: basal forebrain increases, slight cerebral and cerebellar cortex and mesencephalic reticular formation decreases, and no decreases in medial thalamus.
2. We expect **main effects for epoch condition**, indicating significant differences in signal intensity across the three different conditions—TM, passive-attending and mental-counting. These changes may include in rank order: de-excitation will be maximum for TM, then passive-attending, and lastly, mental-counting.
3. We expect **main effects for the repeated measures**, indicating the epoch length that best framed the initial de-excitation of TM practice. For example, longer epoch lengths run the risk of introducing new, and variable cognitive and brain processes. This variability could result in lower signal-to-noise ratio, low signal intensity and more variance in the statistical test.
4. We expect **significant epoch length x epoch condition interactions**. We expect less cognitive and brain variability in the shorter epoch length regardless of condition resulting in greater distinction between epoch conditions. On the other hand, the greater variability of the longer epoch length may diminish the measured difference in signal intensity between conditions.

D.5.5. Outcome.

At the conclusion of this analysis, we should have empirical data sufficient to recommend the epoch length and the control condition to successfully image the initial de-excitation substate of TM practice. Secondary outcomes include consistency of signal intensity for regions of interest within subjects, and variability across runs between subjects. Anatomically, based on previous research-driven neural models (see Sect. B.2.5.), we would expect to at least find cortical de-excitation with possible exceptions of medial and ventral prefrontal cortices, accompanied with some basal forebrain, basal ganglia and brainstem excitation, cerebellar de-excitation and no change in medial thalamic activity.

D.5.6. Conclusion of Aim 1 Experiment.

From this experiment, we expect to find four basic outcomes regarding brain mechanisms during meditation from an ABC-cycling protocol:

- (1) The epoch length that appears to best frame the de-excitation process;
- (2) The effects of two different control conditions;
- (3) The brain areas that appear most closely correlated with the de-excitation process, as measured by the ABC-cycling protocol; and
- (4) The intra- and intersubject variability of activation/deactivation patterns;

Collectively, these findings will help formulate a working model of brain mechanisms during the de-excitation substate of TM practice.

D.6. Examine the Patterns of Neural Activity during the Maximum De-Excitation Substate (Aim 2).

Experiment 2: Comparing BOLD patterns across periods of differing mental & blood-gas conditions

D.6.1. Hypotheses. We will test five hypotheses in this experiment.

D.6.1.1 IBH-Blood Gas Hypothesis. Using event-related-fMRI, we hypothesize moderate changes in blood gas changes will be detected during Intentional Breath-Holding (IBH), and blood gas levels will be significantly correlated with changes in BOLD signal intensity, consistent with published findings.

D.6.1.2 SBQ-Blood Gas Hypothesis. Using event-related-fMRI, we hypothesize small changes in blood gas changes will be detected during Spontaneous Breath Quiescence (SBQ), and blood gas levels will not be significantly correlated with changes in BOLD signal intensity.

D.6.1.3. SBQ-IBH Hypothesis. Using event-related-fMRI, we hypothesize that specific spatiotemporal patterns of BOLD signal will be associated with onset of Spontaneous Breath Quiescence (SBQ), and will

differ from IBH control periods as marked, in particular, by reduced BOLD signal of the anterior cingulate cortex and brainstem during SBQ.

D.6.1.4. SBQ-Controls Hypothesis. Using state-related-fMRI, we hypothesize that BOLD signal intensity patterns during SBQ periods will differ from two control conditions—IBH periods, and eyes-closed periods (as defined in Aim 1, either passive-attending or mental-counting).

D.6.1.5. SBQ-Non-SBQ Hypothesis: Using state-related-fMRI, we hypothesize that BOLD signal intensity patterns during SBQ periods will differ from the scans during non-SBQ periods during meditation.

D.6.2. Issues.

The second phase of the grant will systematically explore neural patterns underlying the second principal substate during TM practice—periods of SBQ with durations of 10 to 40 sec—signifying the maximum de-excited state of TM practice. A study of breath-quietness raises a number of possible confounds.

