The BOLD signal and physiological measures will be collected during four runs of 12 minutes duration each. Each 12 min run comprises three periods: 5 min uninterrupted meditation, 5 min structured breath-holding, and 2 mins non-task, eyes-closed (EC) control. The meditation period are free running with no interruptions from experimenters. During the meditation period we expect 3-5 SBQ periods. The breath-holding periods are structured by duplicating the previous SBQ pattern by voice command from experimenter, the onset and offset of IBH corresponding to SBQs time frame for each subject. The non-task control period will be determined from the outcome of experiment 1 (Aim 1), and either be passive-attending or mental-counting. The physiological measures will include respiration and transcutaneous CO₂ measurements. Four runs will take 48 minutes, or about 1 hr due to 30 rest periods between conditions. Therefore, each fMRI session will last about 90 minutes per subject.

D.6.4. Event-related fMRI analysis (Hypotheses 1-3).

Er-fMRI methodologies will be used to probe brain mechanisms during the onset of two conditions, during SBQ and IBH periods. The scans will be aligned relative to the onset of either SBQ or IBH during the four runs to permit signal averaging: 4 images before (12 secs) and 4 images after onset (12 secs). A TM meditator, selected in our screening protocol, may exhibit 25-30 spontaneous breath-quiet periods in a 30-min TM session [9, 20-22]. We estimate 12-20 periods will occur in our four meditation periods.

Images from individual runs will first be normalized to correct for the range of intra- and inter-subject signal intensity and temporal drift [171]. Specifically, normalization will involve: (1) scaling of signal intensity to a fixed value of 1000; (2) linear slope removal in a voxel-by-voxel basis; (3) spatial filtering with a one-voxel radius Hanning filter, and; (4) removal of the mean signal intensity on a voxel-by-voxel basis. The normalized fMRI images will then be aligned relative to the onset either SBQ or IBH periods. These images will be averaged within each subject. The mean image for each subject will be transformed into stereotaxic atlas space [208] using the highest point of the mid-sagittal plane and the anterior and posterior commissures. The atlas-transformed matrices will then be averaged across subjects.

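### The map analysis assigned to Experiment 1 has no step for slow signal drift in runs of about 22 minutes, although the protocol removes drift in its event-related analysis; the Z maps are miscalibrated by an amount that depends on drift size and epoch order

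*Protocol*

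**What the plan says.** D.5.4 routes Experiment 1 to the standard analysis: "The data will be processed, and clusters of significant fluctuations in signal intensity will be noted (see Sect. D.2.2-D.2.3". The sequence in D.2.2 has five steps. It starts with "discarding the initial three scans of each run due to magnetic instability; (2) correcting for movement artifacts by the co-registration", then registers the images to the anatomy, forms t-maps by multiple linear regression, and converts t to Z. The covariables of that regression are physiological: "The time series from these other physiological variables will be used as real-time covariables in multiple linear regression". D.2.3 accepts areas with Z above 4.0 in clusters of at least four touching pixels, seen in "2 of the 3 statistical parameter maps from multiple runs in the same condition".

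D.5.3 describes the runs: "An ABC-run (for example, using 30 sec epochs) will last about 22min, including 45 total epochs, 15 epochs each condition". On order it says "We will record fMRI (in first 10 subjects meeting inclusion criteria) during randomly ordered epochs of controls and TM practice" and states no restriction.

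D.6.4, for the event-related analysis of the 12-minute runs in Experiment 2, has images first "normalized to correct for the range of intra- and inter-subject signal intensity and temporal drift". One of its listed steps is voxel-by-voxel removal of a linear slope.

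**The concern.** The protocol treats drift as real and specifies its removal for the 12-minute runs, but not for the runs that are nearly twice as long. In a cycling design this matters in two ways.

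- If epoch order is left to chance, TM epochs fall on average somewhat earlier or later in the run than control epochs. A pixel that only drifts then shows a difference between conditions. This is a deterministic trend, separate from scan-to-scan noise correlation. If neighbouring pixels drift together, the four-pixel rule gives little protection.
- Whatever the order, unmodelled drift goes into the residual variance and lowers Z for real effects.

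The Z values of the selected areas are the variate in the MANOVA for Hypotheses 1 and 2. D.5.6 also lists within- and between-subject variability of activation as an outcome.

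**Working it through.** **Inputs from the protocol.** 45 epochs of 30 s, 15 per condition (D.5.3); TR 2.2 s and three scans discarded (D.2.1, D.2.2); threshold Z = 4 (D.2.3); epoch range 20 to 40 s (D.1).

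**The plan's own figure.** 45 × 30 s = 1,350 s = 22.5 min, which agrees with about 22 min. 1,350 / 2.2 = 613 scans, less 3 = about 610.

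**Assumptions not in the protocol.** White noise with SD 1, no true effect, and drift rising by D noise SD over the run.

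**Unrestricted order, hand calculation.**

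1. With N epochs shuffled and N/3 per condition, the gap between the mean positions of two conditions has SD √((N+1)/2) epochs. For N = 45: √23 = 4.80 epochs, or 4.80/45 = 0.107 of the run.
2. Drift D therefore gives a spurious difference with SD 0.107·D.
3. The standard error of a difference between two conditions with about 204 scans each is √(2/204) = 0.099. The ratio is 0.107/0.099 ≈ 1.076 (unrounded).
4. Unmodelled drift multiplies the residual SD by k = √(1 + D²/12).
5. The null variance of Z is then about 1/k² + (1.076·D/k)².

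| D | k | SD of Z | P(abs Z > 4), by hand | P(abs Z > 4), simulated |
|---|---|---|---|---|
| 0.5 | 1.01 | 1.12 | 0.04% | 0.03% |
| 1 | 1.04 | 1.41 | 0.5% | 0.4% |
| 2 | 1.15 | 2.05 | 5.2% | 6.1% |
| 3 | 1.32 | 2.55 | 11.7% | 13.5% |
| 5 | 1.76 | 3.12 | 19.9% | 22.1% |

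The simulation used 3,000 runs per row, with condition regressors convolved with a gamma response. The nominal rate is 0.0063%. For any of the three contrasts, the simulated rates are 0.2% at 0.5 SD, 1.5% at 1 SD, 14.8% at 2 SD and 29.7% at 3 SD.

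**Order random within each ABC set, no drift term.** False exceedance is about 0% for linear and quadratic drift up to 10 SD. The null SD of Z falls to about 0.9 at 2 SD and 0.65 at 5 SD. This is close to 1/k (0.87 and 0.57), so Z for a true effect shrinks in much the same proportion.

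**Epoch length.** Take unrestricted order, equal runs of 22 min and the same drift rate (2 SD per 22.5 min, so D = 1.96 and k = 1.15). With 20-s epochs N = 66 and the gap is √33.5/66 = 0.088 of the run. With 40-s epochs N = 33 and the gap is √17/33 = 0.125. The hand formula gives 2.1% and 8.2% exceedance; simulation gives about 2–3% and 9–10%. If the count of 45 epochs is kept instead, runs last 15 and 30 min, D is 1.33 and 2.67, and residual SD rises by 7% and 26%.

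**Group condition test, 10 subjects, common drift, nominal 5%.** Rejection is 5.2–5.5% if each subject has an independent order. It is 55% at 1 SD and 81% at 3 SD if all share one random order.

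**Which drift term works (unrestricted order).** For linear drift, a linear term brings exceedance back to at most 0.03% for one contrast. For curved drift of 3 SD it does not help: 14.2% (quadratic) and 17.5% (cosine), against 13.6% and 17.0% with no term. A cosine high-pass set at 180 s brings both to about 0.

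**The case against.** The strongest reply is that this is an omission that a separate analysis plan may fill. D.2.2 introduces its steps as what the sequence includes, so the list is not declared complete, and nothing says drift is left in. That stands as far as it goes: the protocol does not forbid a drift term. But it fixes drift removal itself in one analysis and omits it from the fixed sequence of the other, where runs are longer, so the two sections need to be reconciled.

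Second, unrestricted order is one reading only. D.1 speaks of alternating epochs, and D.5.3 gives exactly 15 epochs per condition and refers to comparisons within and across sets; all of this fits balance within ABC sets. This stands. Under balance the false areas go, and the loss of power remains.

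Third, drift size is assumed, and at 0.5 SD or less the effect is small. This also stands.

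Fourth, a reader might infer that the tests of Hypotheses 1 and 2 are biased because they use these Z values. The documents do not support that for the condition test: with separate orders the false effects have random sign and the test keeps its level. Random sign does not protect the selection of areas, the variability outcomes or the epoch-length comparison, where contamination acts on the size and variance of Z.

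Fifth, the 2-of-3-maps rule would cut a 10% rate to 3 × 0.1² × 0.9 + 0.1³ = 2.8% if it applied to independent orders. D.5.3 plans two runs per subject, one per epoch length, so that protection cannot be counted on as written.

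**Conclusion.** The point holds in a conditional form. D.2.2 lists no drift removal for Experiment 1, and D.6.4 shows that drift is expected. Followed as written, the Z maps are miscalibrated on either reading of the epoch order, in opposite directions.

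- Unrestricted order and drift of about 1–2 noise SD or more: too many false areas, about 0.4–6% at 1–2 SD and 13–22% at 3–5 SD for one contrast, against 0.006%.
- Order balanced within ABC sets: almost no false areas from linear or quadratic drift, but Z is too small and power is lost.

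The harm falls on which areas are selected, on the within-subject and variability results, and on the epoch-length comparison of Hypothesis 1. It would be too strong to say that the plan will produce false areas or that the group condition test is invalid. The first needs a drift size and an order that the protocol does not state; the second needs one epoch order shared by all subjects. All figures assume white noise and, unless stated otherwise, linear drift.

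**What to change.** In D.2.2, add per-run drift regressors to the regression for Experiment 1: either linear plus quadratic terms, or a cosine high-pass set with a cut-off well above the mean TM-to-TM interval (3 × 30 s = 90 s at the example epoch length, 120 s with 40-s epochs). The high-pass set is the safer choice, because a quadratic absorbs more complex shapes only in part. Carrying over the linear slope removal of D.6.4 alone would not be enough.

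In D.5.3, state that epoch order is randomised within each ABC set and generated separately for each subject.

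Cost: 2 degrees of freedom per run for the polynomial, or about 2 × 1,350 / 180 = 15 for a 180-s high-pass set, out of about 610 scans. No new data are needed; the order rule must be settled before scanning.
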